6.3.2. Dose Delay/Dose Modification

During the DLT evaluation period of the dose escalation phase, subject can withhold 3D185 due to drug-related AEs. If the withholding time is more than 7 days, the AE will be considered as DLT. Unless DLT occurs, subject's dose of 3D185 will not be reduced during this period.

Treatment can be modified or terminated based on toxicity as described in Table 6. For phosphate, liver, eye, kidney toxicity, specific recommendations in the management guidelines are provided in Section 6.3.1.

Toxicity Grade	Action	Dose Modification After Resolution of Adverse Event
1	None	Continue same dose
2	None or consider withheld or discontinue	If withheld, restart at same dose or 1 dose lower, if necessary.
3	Withheld	Restart at 1 or 2 doses lower if recovery (to \leq Grade 1 or back to baseline for non-hematologic toxicity) is within 28 days. Discontinue drug if unresolved for >28 days.
4	Withheld or discontinue	Discontinue*

Table 6Dose Modification Guidelines

For general toxicity management:

- Subjects with any grade of toxicity (Grade 1 to 4) should be provided symptomatic treatment when applicable.
- Subjects may have more than 1 dose reduction.

- If 3D185 must be withheld for more than 28 days for a drug-related adverse event that fails to resolve to acceptable level (e.g., ≤ Grade 1 non-hematologic toxicity or back to baseline), treatment with 3D185 should be discontinued with the exception noted below.*
- In all cases of clinically significant impaired wound healing or imminent surgery or potential bleeding complications, it is recommended that dose administration be interrupted, appropriate clinical laboratory data be carefully monitored, and supportive therapy administered, where applicable. Dose administration may be restarted when it is considered safe and at an appropriate dose, according to the investigator's assessment.

*Exception: if a subject has been deriving benefit from treatment, and the investigator can demonstrate that re-introduction of study drug is in the best interest of the subject considering the terminal nature of the disease, the drug may be re-introduced at a lower dose and/or intensity if the medical monitor is in agreement with this assessment. With appropriate re-consenting, the subject can be retreated with a 2-dose level reduction as appropriate, along with appropriate clinical follow-up as designated by the investigator.

The interval of withhold treatment should be no more than 28 days. If the interval is more than 28 days due to 3D185 probably unrelated or unrelated AEs or other reasons, it is necessary to discuss with the Sponsor whether it is possible to continue treatment with 3D185.

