If a Grade ≥ 2 drug-related AE occurs during the accelerated titration dose-escalation phase, the i3+3 dose-escalation phase will be initiated earlier. If the i3+3 dose-escalation phase starts from 100 mg, the maximum sample size in this phase will be 30 subjects; and, if i3+3 design starts at the dose of 50 mg or 25 mg, the maximum sample size will be 36 or 42, respectively.

If a subject terminates treatment due to non-DLT reasons during the first treatment cycle, there is no need to replace the subject. When the study has increased to a dose level (d) that is beyond the MTD, and according to the i3+3 decision table (Figure 1), the dose-assignment recommendations in cohorts of d and d-1 are dose de-escalation (D) and escalation (E), respectively, a new cohort may be added between the d and d-1 dose cohort after SMC review and evaluation on the available clinical data of PK/PD, safety, and efficacy, the new cohort can be an intermediate dose cohort (25 mg increment/decrement) or an intermittent schedule (such as 3 weeks on, 1 week off; 5 days on, 2 days off, etc.). The sample size will be increased by 6 subjects accordingly.

This is a decision table for the 3D185 dose-finding study. The target toxicity
probability (pT) is 25% and the equivalence interval (EI) is (16%, 30%) for
42 subjects. Each column represents (n) number of DLT evaluable subjects
treated at the current dose and each row represents (x) number of subjects with
DLTs at the dose level. Each cell in the table provides the dose-assignment
recommendation based on the readouts from the corresponding row (x) and
column (n). The letters in the decision table represent different dose-assignment
recommendations.
At the end of the study, the MTD will be inferred based on the DLT data and all safety data observed at all dose levels. The specific MTD estimation method is shown in Section 4.2. The RPTD will be established by taking into consideration of the PK and/or PD profiles and safety data from the dose escalation phase.
The DLT evaluable subject is defined as the subject who received at least 75% of the planned doses of treatment and completed the safety assessment during DLT evaluation period.
During the DLT evaluation period, subject can withhold 3D185 due to drug-related AEs. If the withholding time is more than 7 days, the AE will be considered as DLT. Subject's dose level of 3D185 will not be reduced during this period unless DLT occurs.
Study Plan and Process
♦ PK Sampling:

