4. STUDY DESIGN AND PLAN

4.1. Overall Plan

This is an open-label, global multicenter, dose-escalation phase 1 study of 3D185 monotherapy in subjects with advanced solid tumors.

The starting dose in this dose-escalation study is 25 mg, and the preset 7 dose-escalation cohorts are 25 mg, 50 mg, 100 mg, 150 mg, 200 mg, 250 mg, and 300 mg, respectively. This study adopts a combination of accelerated titration and i3+3^[1] for dose escalation. All subjects in each cohort will receive a single oral dose of 3D185, followed by a 7-day washout period (i.e. single-dose PK study period). Then, subjects will receive consecutive daily doses (QD, 28 days/cycle) until disease progression, death, unacceptable toxicity, or withdraw of informed consent, whichever comes first. The DLT evaluation period includes the single-dose PK study period and the first treatment cycle (within 35 days after the first dose). The enrolled subjects will be sequentially assigned to the planned dose cohorts according to the protocol, and receive 3D185 treatment to observe the occurrence of DLT:

Accelerated titration dose-escalation phase: One subject is to be enrolled sequentially to 25 mg and 50 mg cohorts, respectively. If no Grade ≥ 2 drug-related AE occurs during DLT evaluation period, the study will escalate to the next dose level. Otherwise, 2 additional subjects will be enrolled, and the subsequent study will convert to i3+3 dose-escalation design from this dose cohort.

In the accelerated titration phase, a subject may be replaced if he/she 1) does not reach to 75% of the total planned dose; 2) discontinued investigational product due to non-DLT reasons during the DLT evaluation period.

i3+3 dose-escalation phase: Starting at 100 mg cohort, 3 subjects are to be enrolled initially at each subsequent dose cohorts in accordance to i3+3 dose-escalation design. Each dose cohort should recruit at least one subject from each country after sites in both countries are activated. If a cohort requires ≥ 6 subjects, it must enroll at least 1 subject from each country and efforts will be made to ensure number of subjects enrolled from each country is similar.

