At the end of the study, the MTD will be inferred based on the DLT data and all safety data observed at all dose levels. The specific MTD estimation method is shown in Section 4.2. The RPTD will be established by taking into consideration of the PK and/or PD profiles and safety data from the dose escalation phase.

The DLT evaluable subject is defined as the subject who received at least 75% of the planned doses of treatment and completed the safety assessment during DLT evaluation period.

During the DLT evaluation period, Subject can withhold 3D185 due to drug-related AEs. If the withholding time is more than 7 days, the AE will be considered as DLT. The subject's dose of 3D185 will not be reduced unless DLT occurs.

4.2. i3+3 Design

Similar to the 3+3 design^[18], the i3+3 is rule-based design, and it is also an interval-based design similar to mTPI^[19]. The specific algorithm of i3+3 design is shown in Appendix 7. Compared to the 3+3 design, the i3+3 design offers greater flexibility (e.g., flexible handling of subject, shedding), higher MTD selection probabilities, and better safety (see Appendix 8 for the comparison results of the simulation trials for 3+3 and i3+3). The target toxicity probability of the MTD in this study is set to pT = 25%, and the equivalence interval (EI) is (16%, 30%). This means

that the MTD should have a toxicity probability near 25% but not below 16% or above 30%. The decision table for the i3+3 design of this study is shown in Figure 1.

[figure not shown]

Figure 1 i3+3 Dose Escalation Decision Table

Note:

This is a decision table for the 3D185 dose-finding study. The target toxicity probability (pT) is 25% and the equivalence interval (EI) is (16%, 30%) for 42 subjects. Each column represents (n) number of DLT evaluable subjects treated at the current dose and each row represents (x) number of subjects with DLTs at the dose level. Each cell in the table provides the dose-assignment recommendation based on the readouts from the corresponding row (x) and column (n). The letters in the decision table represent different dose-assignment recommendations.

The i3+3 dose-escalation phase is expected to enroll 30-42 subjects (maximum sample size will be adjusted according to the first dose entering the i3+3 phase. For details, see Section 4.1). Every 3 subjects as a cohort will be sequentially enrolled.

The specific operation process of i3+3 design is as follows:

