4.5. Dose Limiting Toxicity (DLT) Definition

A DLT is defined as the occurrence of any of the following toxic reactions that are considered to be causally related to 3D185 by the PI within the first 35 days after the first dose.

- 1. Hematological toxicity:
 - 1. Grade 4 hematologic toxicity;
 - 2. Grade 3 febrile neutropenia (defined as ANC < $1,000/\text{mm}^3$, a single temperature of >

38.3 \mathbb{C} or a sustained temperature of \geq 38 °C for more than 1 hour) or Grade 3 neutropenia

lasts for more than 7 days with or without drug intervention;

3. Grade 3 thrombocytopenia with bleeding or require to platelet transfusion;

- 2. Non-hematologic toxicity:
 - 4. Any Grade ≥ 3 non-hematologic toxicity (except the following conditions that can be controlled by symptomatic treatment within 48 hours: nausea, diarrhea, vomiting, and electrolyte imbalance [except serum phosphorus]; Grade 3 fatigue with duration ≤ 7 days; Grade 3 hypertension that can be self-resolved or controlled by drugs to below 140/90 mmHg or baseline level within 72 hours);
 - 5. Serum phosphorus ≥7 mg/dL that is unable to recover to < 7 mg/dL within 14 days after phosphorus removal;
 - 6. With liver metastasis or baseline transaminase abnormalities: ALT/AST > 8 × ULN; without liver metastasis or baseline transaminase abnormalities: ALT/AST > 5 × ULN ;
 - 7. 3D185-related AEs that resulted in dose interruption of 3D185 for \geq 7 days in the first treatment cycle.

If the DLT is clinically recovered to Grade 0-1 within 28 days, the subject can resume the treatment of 3D185. If the subject can resume treatment, the Investigator may refer to the provisions of Section 6.3 (Precautions and Dose Modifications) for dose modifications to the same dose or reduce by one dose level.

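### A drug-related hold of exactly 7 days is a DLT in Section 4.5 but not by the rule in Sections 4.1 and 6.3.2; the in-window ban on dose reduction also needs a stated precedence over Tables 5 and 6

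*Protocol*

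**What the plan says.** **Interruption as a DLT.** Section 4.5 lists as a DLT "3D185-related AEs that resulted in dose interruption of 3D185 for" 7 days or longer (written with a greater-or-equal sign) in the first treatment cycle. The DLT entry of the Synopsis has the same criterion. Section 6.3.2, on dosing in the DLT evaluation period, says "If the withholding time is more than 7 days, the AE will be considered as DLT". Section 4.1 and the design text of the Synopsis repeat that rule. The Synopsis therefore contains both thresholds.

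**Phosphate holds.** Table 4 in Section 6.3.1 withholds drug at a serum phosphate of 7.0 to 9.0 mg/dL until it falls below 5.5 mg/dL, then resumes at the same dose. Its note a suggests an interruption of 7 days.

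**Evaluability.** A DLT-evaluable subject is one who "received at least 75% of the planned doses of treatment and completed the safety assessment during DLT evaluation period" (Section 4.1; Section 9.2.1 matches). Section 4.2 bases the i3+3 recommendation on these subjects only.

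**Dose reduction in the window.** Section 6.3.2 says "Unless DLT occurs, subject's dose of 3D185 will not be reduced during this period". The Synopsis ("Subject's dose level of 3D185 will not be reduced during this period unless DLT occurs") and Section 4.1 ("The subject's dose of 3D185 will not be reduced unless DLT occurs") agree. Table 5 allows a restart only one level lower after Grade 1 keratitis or CSR/RPED, and after any Grade 2 eye toxicity that permits a restart. The Grade 3 row of Table 6 allows a restart only one or two levels lower. Section 4.5 exempts some Grade 3 events from being DLTs, for example those "controlled by symptomatic treatment within 48 hours: nausea, diarrhea, vomiting, and electrolyte imbalance" (phosphorus excepted).

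**The concern.** The DLT count is part of the primary endpoint and the only input to the i3+3 table. If two sections draw the interruption line a day apart, two sites, or a site and the sponsor, can score the same subject differently, and the next cohort's dose can depend on which section was read. A 7-day hold is also the length that the protocol's own phosphate guidance suggests, for a toxicity expected of this drug class.

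The second matter is smaller. For a few toxicities that are not DLTs, the tables list only a lower restart dose while the window rule forbids one. No sentence says which prevails. If a site did reduce, the 75% rule does not say whether doses taken below the assigned level count.

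**Working it through.** **1. Can a 7-day hold be the deciding fact?** Take phosphate of 7.0 to 9.0 mg/dL. Section 8.5.1 grades more than 7 and up to 9 mg/dL as Grade 2, so the Grade 3 criterion is not met. The separate phosphorus criterion in Section 4.5 needs failure to return below 7 mg/dL within 14 days, so a subject who recovers in a week does not meet it. Only the interruption criterion is left. Table 3 schedules chemistry at C1D8 and C1D15. A hold from C1D8 with restart on C1D15 misses C1D8 to C1D14, which is 7 doses.

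**2. Is that subject evaluable?** Planned doses in the window: 1 (single-dose period) + 28 (cycle 1) = 29. Threshold: 0.75 × 29 = 21.75, so 22 doses.

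- 7-day hold: 29 − 7 = 22; 22/29 = 75.9%, evaluable.
- 8-day hold: 29 − 8 = 21; 21/29 = 72.4%, below the threshold on a count of doses.

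The 7-day subject thus enters the i3+3 table, as a DLT or as DLT-free according to the section used.

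**3. Does the i3+3 recommendation change?** Appendix 7, equivalence interval 16% to 30%: escalate (E) if x/n is below it; stay (S) if inside; if above, stay when (x−1)/n is below the interval, otherwise de-escalate (D).

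| Not scored as DLT | Scored as DLT |
|---|---|
| 0/3 = 0%: E | 1/3 = 33.3%, above; 0/3 below: S |
| 1/3: S | 2/3 = 66.7%, above; 1/3 = 33.3% not below: D |
| 0/6 = 0%: E | 1/6 = 16.7%, inside: S |
| 1/6: S | 2/6 = 33.3%, above; 1/6 = 16.7% not below: D |

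The stop-type de-escalation cells (DU) are left out because Appendix 7 does not give their rule and Figure 1 is not legible here.

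**4. The reduction ban.** Suppose Grade 3 vomiting controlled within 48 hours, a 2-day hold after 8 doses, and a restart one level lower as in Table 6. Doses taken: 29 − 2 = 27; 27/29 = 93%. Doses at the assigned level: 8/29 = 28%. The subject passes 75% on a plain count and fails if only assigned-level doses count.

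Removing one such DLT-free subject compares x/n with x/(n−1). Under Appendix 7 no E, S or D cell changes at n = 3, 6, 9 or 12. Changes appear only at irregular sizes: 1/7 (E) to 1/6 (S), 2/7 (S) to 2/6 (D), and 3/10 (S) to 3/9 (D).

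**The case against.** **On the threshold.** Section 4.5 is the titled definition. The sentence in Sections 4.1 and 6.3.2 can be read as a sufficient condition that does not strictly deny that 7 days also counts. Only holds of exactly 7 days are affected, and the SMC sees data on all treated subjects. The narrow reach stands. The rest does not remove the defect: a stated cut-off is normally read as the cut-off, it appears three times, Section 6.3.2 is where a site looks when it holds drug, and nothing says that Section 4.5 prevails.

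**On the reduction ban.** A reader might infer that sites are given two competing dosing orders and that reduced subjects will distort the MTD. The documents do not support this.

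- The ban is mandatory, specific to the window and stated three times. The reference to Table 6 that follows it is permissive, and both tables are titled as guidelines.
- Section 4.5 lets the investigator restart at the same dose even after a DLT. That makes it hard to read the Grade 3 row of Table 6 as a compulsory cut for lesser, exempt events.
- The only scheduled on-treatment eye examination in the window is at C1D28, so most ocular restarts would fall after it.
- A reduced subject reaches the i3+3 table only if a site departs from the ban.
- The other wording of the 75% rule, "does not reach to 75% of the total planned dose", governs replacement in accelerated titration only.

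What stands is that precedence is implied and not written, and that applying the ban literally means a full-dose restart after a resolved retinal event, against Table 5.

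**Conclusion.** The interruption criterion is defined in two ways, and a 7-day drug-related hold in cycle 1 falls between them. The case is realistic, the subject remains evaluable, and the scoring of one subject can move the recommendation by one step at three or six evaluable subjects. This assumes that a 7-day hold means seven missed daily doses and that the threshold is a count of doses. The documents do not say how often such holds will occur, so no effect on the MTD can be quantified.

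The missing precedence between the ban and the tables is a minor drafting gap. It matters mainly for ocular safety. No bias in the MTD is shown, and at the usual cohort sizes removing one such subject changes no recommendation.

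**What to change.** 1. Use one threshold in both places in the Synopsis and in Sections 4.1, 4.5 and 6.3.2. Seven days or more is the stricter choice, but it makes a phosphate hold of the length that Table 4 suggests a DLT. If that is not intended, use more than 7 days throughout. Either way, state that a subject with a DLT is always evaluable, because a hold of 8 days leaves 21/29 (72.4%).
2. Add to Sections 4.1 and 6.3.2 that the ban governs inside the 35-day window, except where Table 5 requires a lower dose for ocular safety.
3. State, there and in Section 9.2.1, that for a subject reduced without a DLT only doses taken at the assigned level count toward the 75%.

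The cost is amendment wording, with no new procedures. The stricter threshold in item 1 may slow escalation through phosphate holds. Item 3 will occasionally remove a DLT-free subject from the denominator, without replacement in the i3+3 phase. That slightly raises the observed DLT rate: 1/6 (16.7%) would become 1/5 (20%), which is still a stay.

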6.3.3. Discontinuation criteria for study treatment

When the following 3D185 related severe or life-threatening AEs occur, the investigational product must be permanently discontinued.

- Drug-related Grade 3 AEs or Grade 2 CSR/RPED that cannot recover to Grade ≤ 1 or baseline levels by symptomatic treatment within 28 days;
- Any grade 4 toxicities;
- Recurrent ≥ 2 Grade proteinuria;
- Recurrent Grade 3 eye toxicity associated with vision changes;
- Hy's law confirmed drug-induced liver injury;
- Grade 2 hypercalcemia concurrent with hyperphosphatemia or ≥ Grade 3 hypercalcemia in absence of hyperphosphatemia;
- Other AEs that the Investigator judged to be inappropriate to continue dosing.

If a subject has been deriving benefit from treatment, and the investigator can demonstrate that reintroduction of study drug is in the best interest of the subject considering the terminal nature of the disease, the drug may be re-introduced at a lower dose and/or intensity if the medical monitor is in agreement with this assessment. With appropriate re-consenting, the subject can be retreated with a 2-dose level reduction as appropriate, along with appropriate clinical follow-up as designated by the investigator.

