> 9.0 mg/dL (> 2.9 mmol/L)	Withhold ^a 3D185 treatment until the serum phosphate level returns to $< 5.5 \text{ mg/dL}$. Resume at the next lower dose level in case of serum phosphate level returns to below 5.5 mg/dL within 7 days. Reduce by two dose levels if it takes 7~28 days to return to below 5.5 mg/dL despite adequate medical management. A second dose reduction may be implemented if needed or clinically indicated for persistent ^b hyperphosphatemia (\geq 7 mg/dL) at every cycle.	Restriction of phosphate intake to 600 – 800 mg/day. Sevelamer up to 1,600 mg 3 times a day with food AND Acetazolamide 250 mg 2 or 3 times a day only until serum phosphate level returns to < 5.5 mg/dL.
> 10.0 mg/dL (> 3.2 mmol/L) or significant alteration in baseline renal function OR Grade 2 hypercalcemia concurrent with hyperphosphatemia	3D185 should be discontinued permanently. (In situations where the subject is having clinical benefit and the investigator and the sponsor's medical monitor agree that re-starting drug is in the best interest of the subject, the drug may be re- introduced at two dose levels lower if appropriate ^c . Follow other recommendations described above.)	Medical management as clinically appropriate.

Note: These are general guidelines that are based on emerging data of other selective FGFR inhibitors and and/or the experts in the field. The treating physicians must use clinical judgment and local standard of care to decide the best way to manage phosphate elevation. If Sevelamer hydrochloride (renagel) is not available, use of other phosphate binders (non-calcium containing) based on the local standard is recommended, including Sevelamer carbonate (Renvela) or lanthanum carbonate (Fosrenol). a. Drug interruptions for hyperphosphatemia suggested to be 7 days duration

b. Persistent hyperphosphatemia is considered to be more than 1 sequential phosphate value of \geq 7 mg/dL c. If a subject has been deriving benefit from treatment, and the investigator can demonstrate that reintroduction of study drug is in the best interest of the subject considering the terminal nature of the disease, the drug may be re-introduced at a lower dose and/or intensity if the medical monitor is in

Serum Phosphate Level	Dose Modification	Medical Management					

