In case of Grade 2 AST/ALT elevation in patients without liver metastasis or AST/ALT elevation \geq 3.0-5.0 folds over baseline value in patients with liver metastasis, withhold 3D185 until the level returns to grade \leq 1 or baseline, and the liver test should be evaluated at least twice a week. Restart treatment with 3D185 at the same dose level.

In case of total bilirubin ≥ 2 folds over ULN, withhold 3D185 until the level returns to CTCAE Grade ≤ 1 or baseline, and the liver test should be evaluated at least twice a week. Restart treatment with 3D185 at same dose level.

In case of Grade 3 AST/ALT elevation, subjects should withhold 3D185 until the AST/ALT level returns to CTCAE Grade ≤ 1 or baseline. If the AE resolves within 7 days, dosing may resume at the same dose level. If the AE resolves within 7-14 days, dosing may resume at the previous lower dose level or may be modified according to the Investigator's judgment. If the AE cannot resolve within 28 days, the treatment of 3D185 will be permanently discontinued. Liver enzymes should be monitored once a week when the subject receives 3D185 treatment again.

When a hepatic injury is suspected due to abnormal liver function test (such as Grade ≥ 3 AST/ALT elevation), it is recommended to perform a comprehensive assessment (liver imaging, liver function tests and pathogen tests, etc.) as soon as possible.

Abnormal values in AST and/or ALT concurrent with abnormal elevations in total bilirubin that meet the criteria outlined below in the absence of other causes of liver injury are considered

potential cases of drug-induced liver injury (potential Hy's law cases) and should always be considered important medical events, 3D185 must be discontinued immediately. The threshold of laboratory abnormalities for a potential case of drug-induced liver injury depends on the subject's individual baseline values and underlying conditions. Subjects who present with the following laboratory abnormalities (potential drug-induced liver injury) should be evaluated further to determine the etiology of the abnormal laboratory values definitively:

- Subjects with AST or ALT and total bilirubin baseline values within the normal range who subsequently present with AST or ALT values ≥ 3 folds over ULN concurrent with a total bilirubin value ≥ 2 folds over ULN with no evidence of hemolysis and an alkaline phosphatase value ≤ 2 folds over ULN.

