- For subjects with preexisting ALT or AST or total bilirubin values above the ULN, the following threshold values should be used in the definition mentioned above:
 - ♦ For subjects with preexisting AST or ALT baseline values > ULN, AST or ALT value ≥ 2 folds over the baseline values and ≥ 3 folds over ULN, or ≥ 8 folds over ULN (whichever is smaller).

Concurrent with:

♦ For subjects with preexisting values of total bilirubin above the normal range: Total bilirubin increased from baseline by an amount of at least 1-fold over ULN or if the value reaches ≥ 3 folds over ULN (whichever is smaller). Exception to the bilirubin elevation is made if the subject has Gilbert's disease and the elevated bilirubin is predominantly unconjugated.

The subject should return to the investigational site and be evaluated as soon as possible, preferably within 48 hours from awareness of the abnormal results. This evaluation should include laboratory tests, detailed history, and physical assessment. It is highly recommended to consult a hepatologist. The possibility of hepatic neoplasia (primary or secondary) should be considered. In addition to repeating measurements of AST and ALT, laboratory tests should include albumin, creatine kinase, total bilirubin, direct and indirect bilirubin, gamma-glutamyl transferase, PT/INR, and alkaline phosphatase. A detailed history, including relevant information, such as review of ethanol, acetaminophen, recreational drug, and supplement consumption, family history, occupational exposure, sexual history, travel history, history of contact with a jaundiced person, surgery, blood transfusion, history of liver or allergic disease, and work exposure, should be collected. Further testing for acute hepatitis A, B, or C infection and liver imaging (e.g., biliary tract) may be warranted. All cases confirmed on repeat testing as meeting the laboratory criteria defined above, with no other cause for Liver Function Test (LFT) abnormalities identified at the time should be considered potential drug-induced liver injury event. Such potential drug-induced liver injury should be reported as SAEs. When there is no other reason to explain the elevation of liver enzymes (Hy's law confirmed), 3D185 must be permanently discontinued.

♦ Nephrotoxicity (Proteinuria) Management Guideline

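### Section 6.3.3 allows re-introduction of 3D185 after confirmed Hy's law liver injury, which Section 6.3.1 stops permanently without exception

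*Protocol*

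**What the plan says.** **Section 6.3.1, Hepatotoxicity Management Guideline.** Potential Hy's law cases are to be treated as "important medical events, 3D185 must be discontinued immediately". If no other explanation for the enzyme elevation is found, the guideline closes the matter: (Hy's "law confirmed), 3D185 must be permanently discontinued". No exception, footnote or route back to treatment is attached.

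**Section 6.3.3, Discontinuation criteria.** The list opens with "When the following 3D185 related severe or life-threatening AEs occur, the investigational product must be permanently discontinued". One of its seven items is Hy's "law confirmed drug-induced liver injury". The paragraph directly after the list says that "the drug may be re-introduced at a lower dose and/or intensity if the medical monitor is in agreement with this assessment". Its conditions are:

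- the subject has been benefiting;
- the investigator can show that restarting is in the subject's best interest;
- the medical monitor agrees;
- the subject re-consents;
- the dose and/or intensity is lower, with a two-level reduction as appropriate;
- the investigator sets the clinical follow-up.

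The paragraph does not say which listed events it covers, and it excludes none.

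**Section 6.3.2, Table 6.** A starred exception in nearly the same words is attached to Grade 4 toxicity and to drug-related events that keep treatment on hold for more than 28 days. It has no liver exclusion either. Section 6.3.2 also refers readers to 6.3.1 for specific phosphate, liver, eye and kidney recommendations.

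**The concern.** Two sections of the same protocol give different answers for the same event. An investigator who follows 6.3.1 may not restart. An investigator who follows 6.3.3, with the medical monitor's agreement and a new consent, may restart and can say that the protocol was followed.

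The stake is subject safety. Under 6.3.1, Hy's law is confirmed only when no other cause has been identified, so re-introduction means re-exposure to the agent held responsible. The liver is a recognised concern for this drug. Section 2.2.1.3 reports liver function changes among the rat repeat-dose toxicities, Section 2.3 lists raised transaminases with similar drugs, and Section 6.3.1 names liver function abnormalities as a possible toxicity of 3D185.

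**Working it through.** No figure in the plan depends on this point, so the check compares texts. One threshold is worked through in step 4.

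**1. Does the permission in 6.3.3 reach Hy's law?** The item is on the list, the paragraph follows the list directly, and the paragraph's function is to relax it. Nothing in the paragraph limits its scope by event. On its wording, it reaches Hy's law.

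**2. Does 6.3.1 contain a matching exception?** No. Where 6.3.1 allows a restart after a permanent stop, it ties the permission to named events:

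- Table 4 does so for phosphate above 10 mg/dL, a significant change in renal function, or Grade 2 hypercalcemia with hyperphosphatemia, if the investigator and medical monitor agree that "re-starting drug is in the best interest of the subject".
- Table 5 does so for certain Grade 2 and Grade 3 eye events.
- The liver guideline has no such clause.

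**3. Does any clause rank the sections?** The only candidate is the sentence in 6.3.2 referring liver toxicity to 6.3.1. It belongs to the Table 6 dose-modification rules, 6.3.3 does not repeat it, and it does not say that 6.3.1 overrides 6.3.3. Section 6.3.3 also names Hy's law itself, so it is not merely a general rule silent on the event.

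**4. Would other liver rules require recovery before a restart?** Two general hold rules in 6.3.1 are relevant.

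- *Bilirubin.* At total bilirubin of at least 2 × ULN, the drug is held until Grade 1 or lower, or baseline, with liver tests at least twice a week. Every Hy's law case as defined in 6.3.1 meets this trigger. If baseline bilirubin is normal, the definition itself requires at least 2 × ULN. If baseline bilirubin is above ULN, the definition requires either a rise of at least 1 × ULN, which gives more than 1 × ULN + 1 × ULN = 2 × ULN, or a value of at least 3 × ULN. Both exceed 2 × ULN.
- *Grade 3 AST/ALT.* Where that grade is reached, "subjects should withhold 3D185 until the AST/ALT level returns to CTCAE Grade" 1 or lower, or baseline. After a restart, "Liver enzymes should be monitored once a week when the subject receives 3D185 treatment again".

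These rules are written for ordinary holds; the bilirubin rule, for example, ends in a restart at the same dose. Whether they still govern a subject who has been permanently stopped under Hy's law is not stated. Nothing in 6.3.3 switches them off, and nothing in 6.3.3 invokes them.

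**5. Result.** For confirmed Hy's law injury, 6.3.1 gives a permanent stop without exception, and 6.3.3 gives a permanent stop with a conditional route back. The texts conflict, and no rule of precedence resolves them.

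**The case against.** The strongest defence is that the organ-specific rule controls. Section 6.3.2 sends liver toxicity to 6.3.1, and 6.3.3 is permissive, so a site that obeys 6.3.1 breaches nothing. This is a sensible reading and many investigators would adopt it. It is not written down, however, and the permissive wording still allows another investigator to restart within the protocol.

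A second defence is that a stop followed by an exception is the protocol's deliberate pattern (Tables 4, 5 and 6, and 6.3.3), with real safeguards. The investigator must make the case, the medical monitor must agree, and the subject must re-consent. Potential drug-induced liver injury is also reported as an SAE, to the sponsor within 24 hours (Section 8.7.1), so a rechallenge would not go unseen. All of this stands and makes the scenario rare. None of it excludes Hy's law.

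A reader might infer that the protocol allows restart with no liver-recovery condition at all. The documents do not support that. The bilirubin hold covers every Hy's law case as defined, and the Grade 3 AST/ALT hold applies where that grade is reached, so recovery may still be required. The narrower statement is that 6.3.3 sets no liver condition of its own. The starred exception under Table 6 does not settle the question. It is attached to events that fail to resolve, but also to Grade 4 in a column headed for action after resolution.

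**Conclusion.** The conflict is real and worth correcting. Section 6.3.1 denies rechallenge after confirmed Hy's law injury, Section 6.3.3 permits it on stated conditions, and nothing says which prevails. The conclusion assumes that the 6.3.3 paragraph applies to the list it follows, which is its natural reading.

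The size is limited. One listed event is concerned, the protocol gives no Hy's law rate, and the procedural conditions make use of the clause unlikely.

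A reader might extend the point to the other listed stops. That is not supported here: Table 4 writes an exception for Grade 2 hypercalcemia with hyperphosphatemia, Table 5 for certain eye events, and Table 6 for Grade 4 toxicity in general. Nor does the point touch the dose-finding. DLT counting, i3+3 decisions and MTD selection are the same whichever section is followed.

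**What to change.** Add one sentence to the re-introduction paragraph in 6.3.3 and to the starred exception under Table 6: *Re-introduction does not apply to confirmed Hy's law drug-induced liver injury.*

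The cost is one sentence in two places, made by amendment, with no change to design, sample size or data collection. The downside is that a rare subject who is benefiting loses the option of rechallenge, which 6.3.1 already denies.
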